#### *Medical Monitoring:*

There will be a physician who will provide medical monitoring of the body composition and metabolic blood chemistry appointments.

i        **Investigator only**

ii        **Independent expert to monitor**

Not applicable

iii        **Institutional Data and Safety Monitoring Board**

To ensure that participants are medically stable and safe to participate in the project, physician's approval and a signed release will be required prior to the initial assessment. During assessment and exercise sessions, participants will be monitored for safety, pain, and any signs of distress. Heart rate monitors will be worn during the VO2 testing. Blood pressure will be taken at the beginning of all testing and intervention sessions. If a participant reports an 8/10 pain level prior to a session, the session will be canceled and rescheduled. If at the end of a session the participant reports pain 8/10 or higher, the rating will be documented in the study's adverse event tracking log. Participants may be dismissed from participation if they rate pain 8/10 or higher over three consecutive sessions. Trained research investigators will be present during all sessions to ensure participant safety. If a participant is uncomfortable with having their blood drawn for metabolic testing, they may choose to skip that portion and still continue within the study. All members of the research team are familiar with potentially dangerous conditions associated with SCI, such as autonomic dysreflexia, and will take appropriate actions if a

---

participant experiences a medical emergency. Adverse events will be reported to the IRB consistent with the IRB's reporting guidelines. We will take every precaution to ensure participant safety while avoiding risks.

**Safeguarding of data:** Researchers will assign participants a code to de-identify all data according to HIPAA policies. Data will be stored in a password-protected computer to guarantee participant privacy. To ensure quality of data collection, a research member will oversee each piece of equipment (i.e., Metabolic cart, heart rate monitor, and accelerometers) for immediate detection of technological malfunctions during sessions.

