### **C3 Rationale for the Selection of Outcome Measures**

The primary outcome variables for this randomized controlled trial (RCT) include: cardiorespiratory fitness (VO2peak and 6-minute push test), pain (Wong-Baker FACES), metabolic health (blood chemistries), body composition (dual-energy x-ray absorptiometry [DXA] scan, height, weight, BMI), vitals (heart rate and blood pressure), and psychosocial well-being (PROMIS-29 Profile). These variables are significantly impacted by physically inactive lifestyles, which are highly common among manual wheelchair users (MWUs) with SCI. MWUs with SCI also exhibit and report values of some of these variables below healthy range, potentially impacting physiological health and psychosocial well-being and overall quality of life. Secondary outcome variables

---

include qualitative perspectives of the research staff delivering the exercise intervention and of participants to assess the feasibility of the intervention protocol.

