**2.f Early Withdrawal of Subjects**

Participants (CBEI or EEG) will be withdrawn if they are non-compliant with the exercise program specific to their group assignment (miss >30% of visits in a particular month) or if they experience a medical complication that prohibits exercise.

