**2.h Data Collection and Follow-up for Withdrawn Subjects**

Whether participants withdraw voluntarily or are withdrawn by research staff, they may be asked to complete a close-out visit (in-person or on the phone) to provide the research team with feedback regarding why they decided to leave the study early/not comply with the program.

---

As this is a pilot RCT, if a participant is withdrawn, initial assessment data will be evaluated; however, no follow-up assessment will be conducted.

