## ***G5 Missing Outcome Data***

Only complete, valid data will be included in group analysis for each outcome measure for each participant. While missing outcome measure data will be excluded from group analysis, individual incomplete, invalid, or missing data may be analyzed on a case-by-case basis to potentially further inform the study process and explain participant outcomes.

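### The pain-dismissal rule can in practice act before T2 only in the exercise arm; if dismissed people lose T2, the T2 pain comparison tilts slightly towards that arm

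*Combined protocol and SAP*

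**What the plan says.** **The rule.** F6, 6.a (under item iii) provides for pain monitoring at assessment and exercise sessions. If a participant reports pain of 8/10 beforehand, "the session will be canceled and rescheduled". Pain of 8/10 or more at the end of a session goes into the adverse event log. Then: "Participants may be dismissed from participation if they rate pain 8/10 or higher over three consecutive sessions". The rule is worded for all participants and is discretionary. It does not say whether a dismissed person still attends T2.

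**Follow-up and analysis.** 2.h opens "Whether participants withdraw voluntarily or are withdrawn by research staff", offers a close-out visit for feedback, and says that for a withdrawn participant "no follow-up assessment will be conducted". G5 adds: "Only complete, valid data will be included in group analysis for each outcome measure for each participant".

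**General withdrawal.** 2.f applies to both arms: "Participants (CBEI or EEG) will be withdrawn if they are non-compliant with the exercise program specific to their group assignment", "or if they experience a medical complication that prohibits exercise". Pain dismissal is not among its grounds.

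**Contacts before T2.** E1 gives CBEI 36 sessions over 12 weeks, with pain assessed at the start and end of each. The education arm (EEG) has one educational session, for which no pain rating is described, and weekly calls whose listed topics do not include pain. J4 places the EEG gym membership after the first 12 weeks. Under 2.d, randomisation follows the initial assessment (T1), so ratings taken then are common to both arms.

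**Pain as an outcome.** Pain is in the A2 hypothesis. C3 lists the Wong-Baker FACES scale among the primary outcome variables. F3 includes PROMIS pain interference and pain intensity among the T1 measures, and F4 repeats T1 at T2. F3 does not name FACES.

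**The concern.** A rule that removes people for high pain, and can in practice reach only one arm, acts directly on a planned comparison. If the people removed have no T2 data, the CBEI group that is left reports less pain at T2 than the group that was randomised, while EEG keeps its high-pain members. The comparison would then favour CBEI even if the programme did nothing for pain. G4 plans both an unadjusted and a baseline-adjusted comparison for outcomes other than VO2peak, so both would be affected. G1 wants the pilot's data for sizing a larger trial, and a shifted pain estimate would carry over into that work. There is also a practical gap: staff who dismiss someone under 6.a are not told whether to book T2.

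**Working it through.** The documents give no pain SD, correlation or dismissal rate and no power calculation, so there is no stated figure to reproduce. The values below are assumptions, shown with ranges.

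**Step 1. Can the rule act in EEG before T2?** It needs ratings at three consecutive sessions. CBEI has 36 rated sessions. EEG has at most the two T1 days, which precede allocation, and one educational session with no rating described. In practice, no.

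**Step 2. Size after k dismissals, 20 per arm, no treatment effect.** Remove the k CBEI people with the highest session pain. Let m be the sum of the expected k largest of 20 standard normal values, divided by (20 − k). The expected three largest are 1.867, 1.408 and 1.131.

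- k = 1: m = 1.867/19 = 0.098
- k = 2: m = 3.275/18 = 0.182
- k = 3: m = 4.406/17 = 0.259

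Unadjusted bias = −r(session,T2) × m. Baseline-adjusted bias ≈ −[r(session,T2) − r(session,base) × r(T2,base)] × m. With all correlations 0.6, the multipliers are 0.6 and 0.6 − 0.36 = 0.24. The simulation used 40,000 to 100,000 trials per scenario.

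| Dismissed | Unadjusted, formula | Unadjusted, simulated | Adjusted, formula | Adjusted, simulated | Simulated adjusted bias / its SE |
|---|---|---|---|---|---|
| 1 | −0.059 | −0.058 | −0.024 | −0.023 | 0.023/0.259 = 0.09 |
| 2 | −0.109 | −0.107 | −0.044 | −0.043 | 0.043/0.263 = 0.16 |
| 3 | −0.156 | −0.158 | −0.062 | −0.067 | 0.067/0.268 = 0.25 |

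Units are SD of T2 pain; a negative value means lower pain in CBEI. If session pain ranked people exactly as T2 pain does, the simulated unadjusted figures would be −0.097, −0.179 and −0.258.

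**Step 3. Direction.** The unadjusted bias favours CBEI whenever session pain and T2 pain are positively correlated. The adjusted bias depends on the bracket in Step 2. With r(session,T2) = 0.6 and both baseline correlations equal to r, the bracket is 0.6 − r², which is zero at r = √0.6 = 0.775. For two dismissals the simulated values are:

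| r | 0.3 | 0.5 | 0.6 | 0.7 | 0.775 | 0.8 |
|---|---|---|---|---|---|---|
| Adjusted bias (SD) | −0.095 | −0.066 | −0.043 | −0.021 | 0.000 | +0.008 |

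**Step 4. Offsets from 2.f.** All correlations 0.6, two CBEI dismissals:

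- 2.f also removes the highest-pain EEG person: −0.051 unadjusted, −0.022 adjusted.
- 2.f removes the two highest-pain EEG people: −0.002 and −0.001.
- 2.f would have removed one of the two CBEI people anyway: 6.a adds 0.109 − 0.059 = 0.050 unadjusted and 0.044 − 0.024 = 0.020 adjusted.

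**Step 5. A model closer to the written rule.** Ratings on 0–10, autocorrelated over 36 sessions, trigger of three consecutive ratings of 8 or more, dismissal probability 0.5 or 1 once triggered. The bias favoured CBEI in all 18 scenarios.

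| Assumed mean pain | Expected dismissals of 20 | Unadjusted bias (SD) | Adjusted bias (SD) |
|---|---|---|---|
| 3–4 | 0.3–3.3 | 0.02–0.23 | 0.01–0.09 |
| 5 | 2.2–6.0 | 0.12–0.38 | 0.03–0.16 |

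**Step 6. Chance that it never arises.** For a per-person dismissal chance of 1%, 5% or 10%, the probability of no CBEI dismissal is 0.99^20 = 82%, 0.95^20 = 36% or 0.90^20 = 12%.

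**The case against.** **It is not a separate defect.** The bias exists only because 2.h ends follow-up and G5 uses complete data; 6.a itself does not forbid T2. This largely stands. The point is one route within a wider issue and can be merged with a general point on 2.h and G5. It needs its own cross-reference because 2.f does not name pain dismissal, so a repair confined to 2.f might not reach it.

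**The 8/10 reschedule rule may also cover assessment days.** The 6.a paragraph speaks of assessment and exercise sessions together. On that reading, same-day T2 pain is capped in both arms. Modelling this cut the bias by 25–28% unadjusted and 13–22% adjusted. Other ways of modelling the cap gave reductions of up to 46% and 34%. It never vanished, and the cap would act less directly on PROMIS.

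**FACES at T2 is not established.** This stands. PROMIS pain is the documented two-arm measure at T2, and its correlation with session ratings is unknown.

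**The modelled selection is not exactly the rule.** If cancelled sessions do not count, the rule mainly catches end-of-session pain, possibly provoked by exercise. How well that predicts T2 pain is unknown, and the assumed 0.6 could be too high.

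**EEG safety contact.** 6.a mentions weekly contact about the safety of EEG participants, although G2 has a near-identical sentence about CBEI. Even if the 6.a wording is right, no repeated session ratings are described for EEG.

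**Conclusion.** The point holds as a minor one. The rule can in practice dismiss people before T2 only from CBEI, and on the natural reading of 2.h and G5 those people leave the analysis of a listed outcome. The expected tilt towards CBEI in T2 pain is about 0.06 to 0.16 SD unadjusted and 0.02 to 0.07 SD adjusted for one to three dismissals, under assumed correlations of 0.6. That is at most a quarter of a standard error for the adjusted analysis. It could be larger in a high-pain sample with the rule firmly enforced. It is smaller if the reschedule rule applies at T2 in both arms or if 2.f removes high-pain EEG people, and zero if nobody is dismissed.

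A reader might infer more than the documents support:

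- **That the protocol says dismissed people lose T2.** It does not. This follows from reading dismissal as withdrawal by staff under 2.h.
- **That the bias always favours CBEI.** The adjusted bias is about zero at baseline correlations near 0.77 and reverses slightly above that.
- **That the primary result is affected.** VO2peak, which G4 names as primary, is not directly selected on.
- **That poor tolerability would be hidden.** The adverse event log, the close-out visit and the interviews with people who drop out would still record it.

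**What to change.** State in 2.h, with a cross-reference in 6.a, that dismissal for pain ends the exercise sessions but not study follow-up. Collect T2 from these people where safe: at minimum the PROMIS pain measures, by phone if needed and with that option open to either arm, plus FACES if it is confirmed as a T2 measure. Analyse them in the arm to which they were randomised, and report the number dismissed for pain by arm. If 2.h is revised to keep follow-up for all withdrawals, 6.a needs only the cross-reference. The 8/10 threshold and the discretion to stop exercise stay as they are.

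The cost is a sentence, a cross-reference and a few extra T2 contacts. For those reached by phone, the mode differs from the in-person T2, and a verbal pain rating is not equivalent to the FACES scale.

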**iv      Independent Data and Safety Monitoring Board**

Not applicable

**6.b    Definitions of Adverse Events**

An adverse event will be defined as a musculoskeletal injury, episode of autonomic dysreflexia, or other medical event that is the result of the assessments or exercise training program.

**6.c    Classification of Events**

**i      Relationship**

**ii      Severity**

Any event that requires medical care will be defined as an adverse event.

**iii     Expectedness**

Adverse events are not expected as a result of the intervention.

**6.d    Data Collection Procedures for Adverse Events**

Adverse events will be recorded in an adverse event tracking log and reported in publications resulting from data.

**6.e    Reporting Procedures**

Adverse events will be reported to the IRB consistent with the IRB's reporting guidelines and will be reported to the National Institutes of Health upon annual progress reports.

**6.f    Adverse Event Reporting Period**

Consistent with the IRB's reporting guidelines.

**6.g    Post-study Adverse Event**

All adverse events will be examined at the completion of the study.

***F7   Study Outcome Measurements and Ascertainment***

---

## **G Statistical Plan**

### **G1 Sample Size Determination and Power**

This is a pilot study, with our primary interests in outcome variability and co-variability and estimates of feasibility and acceptability, which will aid in the planning of a larger trial. The sample size of 40 participants was selected to provide enough participants to assess the research protocol, determine trends in change, and provide data to calculate sample sizes for a larger RCT.

### **G2 Interim Monitoring and Early Stopping**

The research coordinator is the primary scheduler for initial and post-assessments and CBEI sessions; therefore, she will daily monitor assessments and CBEI safety, compliance, and progress/stopping. The research coordinator will also be in weekly contact with designated PQHWC staff to update the research team on the safety and compliance of CBEI participants. Designated PQHWC staff will be present to supervise all CBEI participants to monitor safety.

### **G3 Analysis Plan**

The proposed project utilizes a mixed method approach. The *Primary Aim* is an experimental strategy using an RCT method to estimate improvements in physical function, cardio-metabolic health, and psychological well-being of participants enrolled in a community-based exercise intervention compared to an education-only control group on people with SCI. This is a pilot study with the purpose of determining the feasibility of implementing an RCT intervention and developing methodology together with protocols for a larger study with longer-term follow-up assessments. The proposed project utilizes a mixed methods approach, with the *Secondary Aim* being both quantitative and qualitative in nature to evaluate the feasibility of the intervention and evaluate the methods of delivery from the perspective of the research staff conducting and monitoring exercise sessions and the participants regarding the enrollment, assessment, and acceptance, adherence, and tolerance of the intervention protocol.

### **G4 Statistical Methods**

*Aim 1:* Data will be collected and managed using Research Electronic Data Capture (REDCap) and exported to SPSS for analysis. Descriptive statistics will be used to describe the CBEI and the EEG. The data will be examined for normality, outliers, and errors. To examine whether the datasets meet the assumptions of normality, a Shapiro-Wilks test will be conducted. The assumptions of homogeneity of variance and homogeneity of covariance will be examined with Box's M and Mauchly's W tests, respectively. To examine the presence of outliers, histograms will be used. The purpose of the analysis is to compare the post VO2peak measures (primary outcome) between the two groups. First, a two sample t test (or non-parametric Wilcoxon test) will be used for unadjusted analyses. Then we will use a linear regression to compare VO2peak between the CBEI and EEG, adjusting for pre-VO2peak measures and other potential covariates. For other outcomes, based on the measurement scale, a similar analysis approach (unadjusted and adjusted) will be used. For binary outcomes, a Pearson Chi-square or fisher exact test will be used for unadjusted analyses, and a logistic regression model will be used for adjusted analyses. For continuous outcomes, we will perform

---

analyses similar to those of the VO2peak outcome. Additionally, effect size (d) associated with the intervention will be calculated using Cohen's *d* and will be interpreted as small (*d* ≤ .2), moderate (*d* ~ .5), or large (*d* ≥ .8). We will explore whether results differ depending on level of SCI and length of time living with an SCI. We will use dummy variables for these two variables and test the interaction term (intervention-by-the-dummy) in the model.

**Aim 2:** We will use descriptive statistics to report on scales collected during and after sessions to further understand acceptability, feasibility, and fidelity. Our qualitative interviews will allow us to further explore whether patterns can be identified in participants who achieved improvement versus those who did not and those who dropped out of the study. Interview data will be transcribed, processed using NVivo, and analyzed using an adaptation of grounded theory analysis, which will include four steps to be employed iteratively: (1) open coding, in which particular concepts in the transcripts are identified and grouped into categories; (2) axial coding, in which categories are associated and related by conditions, actions/interactions, and consequences; (3) process coding, in which concepts and categories are examined in changing circumstances; and (4) selective coding, in which conceptual models and theories are developed, integrated, and refined.

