## A Introduction

### A1 Study Abstract

Persons with spinal cord injury (PwSCI) are at a greater risk for major health conditions and poorer health outcomes than persons without spinal cord injury. For PwSCI, habitual exercise is critical for both physiological and psychological well-being. Prior research indicates that exercise programs conducted in a controlled setting have positive effects on the physical and psychosocial fitness of PwSCI, but the efficacy and feasibility of these programs are not well understood in community-based settings. PwSCI will be randomized to a 12-week community-based exercise intervention (CBEI; n = 20) or an exercise education control group (EEG; n = 20). The proposed project aims to examine

---

potential health benefits in response to the intervention and identify the barriers and facilitators to successful implementation of a CBEI in PwSCI (N = 40).

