## **2.d Randomization Method and Blinding**

Randomization does not occur until after the initial assessment is completed. Immediately following completion of the initial assessment, each participant will be randomly assigned to either the CBEI ( $n = 20$ ) or EEG ( $n = 20$ ). To control for selection bias, stratified randomization will be used to ensure that the CBEI and EEG are balanced with respect to how long the participant has been injured ( $<2$  years or  $\geq 2$  years), the participant's level of injury (below C7 or C7 and above), age ( $<40$  years or  $\geq 40$  years of age), and gender. This will control for a large imbalance of participants allocated to one intervention. Research staff performing the assessments will be blinded to group randomization.

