### **Self-Report Assessments:**

*Characteristics of Respondents (CORE):* The following data will be collected via the CORE: demographics (age, gender, race, employment status, and highest level of education completed), diagnosis, neurological level of injury, time since onset of injury, general health status, secondary health conditions, medications, and mobility device used.

*PROMIS Measures:* The PROMIS measures will be used to assess six different domains: emotional distress, emotional support, sleep, pain interference, pain intensity, and fatigue. Individuals respond to the items in each domain using a five-point Likert scale. The six domains are scored individually.

*Leisure Time Physical Activity Questionnaire for People with SCI (LTPAQ-SCI):* The LTPAQ-SCI is a self-report measure of leisure time physical activity that assesses minutes of mild, moderate, and heavy intensity activity over the previous seven days. The survey will be collected during screening to determine eligibility.

*The SCI Exercise Self-Efficacy Scale (ESES):* The ESES is a 10-item, SCI-

---

specific scale developed to measure perceived exercise self-efficacy for various types of physical activities. The scale requires individuals to self-report their confidence in performing physical activities and exercise. One dichotomous item asks whether the individual has exercised at home and/or in a gym in the past 12 months. Individuals respond to the 10 items using a four-point Likert scale (1: not at all true, 4: always true); the total score is then derived by summing the scores for the individual items; scores range from 10 to 40. Higher scores indicate greater perceived self-efficacy. The dichotomous item is used to estimate the participant's average exercise activity.

**Community Participation Index (CPI):** The CPI is a valid and reliable assessment of involvement in life situations and individual control over participation. For each item, respondents rate frequency (either in days, hours, or times per week, depending on the activity), whether it was important (yes/no), and to what extent they do the item (too much, enough, or not enough). The measure is used as a categorical variable using validated scores. Participation will be assessed at baseline and both follow-up assessments to determine the level of change in participation for each MWU with SCI.

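### The exploratory moderator analysis reduces time since injury to a dummy and names only an interaction test; a continuous term reported with confidence intervals would use the data better

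*Combined protocol and SAP*

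**What the plan says.** G4 Statistical Methods introduces the analysis as exploration: "We will explore whether results differ depending on level of SCI and length of time living with an SCI". It then gives the method: "We will use dummy variables for these two variables and test the interaction term (intervention-by-the-dummy) in the model". It states no cut-point or number of categories, and for the moderators it names no interval or subgroup estimate.

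The baseline CORE questionnaire (F3 Visit 1, Self-Report Assessments) lists "neurological level of injury, time since onset of injury" among its items. The form itself is not in the documents; L4 says the questionnaires are attached to the IRB application.

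The only cut for time since injury is in section 2.d, where randomization is stratified so that the arms are "balanced with respect to how long the participant has been injured", at under 2 years versus 2 years or more. The same section splits injury level at C7.

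G1 gives no power calculation for any test: "The sample size of 40 participants was selected to provide enough participants to assess the research protocol". The design is 20 per arm. G5 analyses complete data only, and section 2.h plans no follow-up assessment after withdrawal.

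**The concern.** There are two separate issues.

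- **Coding.** Time since injury is a duration. A two-level dummy treats everyone on the same side of the cut as alike. If the benefit of the exercise programme changes gradually with time since injury, this discards information already collected. As G4 names no cut, the coding could also be settled after the data are seen.
- **Output.** The only step named is a test of the interaction term. In a two-arm trial of 40 such a test is imprecise, so non-significance is likely unless the true difference is very large. Nothing in G4 warns against reading that result as evidence that the programme works equally well for everyone. An estimate with its interval would show how little is known.

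**Working it through.** The plan has no figure of its own to reproduce, because N = 40 is given without a power calculation.

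**Inputs from the documents.** N = 40, allocated 1:1; dummy coding with an intervention-by-dummy term; adjustment for baseline VO2peak (G4).

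**Assumptions.** Two-sided alpha 0.05 and 80% power; a two-level dummy; share p below the cut of 50% or 20%; baseline-to-post correlation r from 0 to 0.9. Effects are in SDs of post-intervention VO2peak. All 40 are analysed unless stated.

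**1. Information kept by the dummy.** For an effect linear in the moderator, this is the squared correlation between the dummy and the continuous variable. For a normal moderator it is φ(z_p)² / [p(1−p)].

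- 50/50: 0.399² / 0.25 = 0.64, so 36% is lost.
- 20/80: 0.280² / 0.16 = 0.49, so 51% is lost.

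Other distributions:

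- Uniform: 3p(1−p) is kept. That is 0.75 at 50/50 (25% lost) and 0.48 at 20/80 (52% lost).
- Exponential, with cut c in units of the mean and p = 1 − e^(−c): c²(1−p)/p is kept. That is 0.693² × 1 = 0.48 at 50/50 (52% lost) and 0.223² × 4 = 0.20 with 20% below the cut (80% lost).

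If the effect steps exactly at the cut, the dummy is the correct model and nothing is lost.

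**2. Precision of the interaction.** Main-effect SE = √(4/N) = √(4/40) = 0.316. Interaction SE = √(4 / [N p(1−p)]). The ratio of the two is 1/√[p(1−p)], which is smallest, at 2.0, when p = 0.5.

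- 50/50: √(4/10) = 0.632, ratio 2.0.
- 20/80: √(4/6.4) = 0.791, ratio 2.5.

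Detectable difference = (1.96 + 0.84) × SE, multiplied by √(1−r²) when adjusted for baseline:

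| | 50/50 | 20/80 |
|---|---|---|
| r = 0 (unadjusted) | 1.77 SD | 2.21 SD |
| r = 0.7 (factor 0.714) | 1.27 SD | 1.58 SD |
| r = 0.9 (factor 0.436) | 0.77 SD | 0.97 SD |

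The unadjusted main effect for comparison is 2.80 × 0.316 = 0.89 SD. G4 itself labels d of 0.8 or more as large. With 34 complete cases, the unadjusted 50/50 figure rises to 1.92 SD.

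**3. What continuous coding recovers.** With time in SD units, the change in treatment effect per SD of time has SE √(4/40) = 0.316, so the detectable slope is about 0.89 SD per SD of time, unadjusted. Under a normal moderator and a linear effect, the dummy needs a steeper slope by a factor of 1/√(information kept): 0.89/√0.64 = 1.11 at 50/50 and 0.89/√0.49 = 1.27 at 20/80. The gain is real, but a slope of 0.89 is still very steep.

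**The case against.** G4 calls this exploration, in a pilot whose stated purposes (G1, G3) are variability, feasibility and methods for a larger trial. Using the stratification factor as the subgroup variable is a conventional choice and consistent with the design. A regression interaction also yields a coefficient, and the primary aim is worded as estimation, so the plan does not rule out reporting estimates. An interaction SE at least twice the main-effect SE is a feature of any 1:1 two-arm trial. A log-linear trend replaces one assumption with another, which 40 people can check only roughly. All of this stands, and it makes the point small.

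A reader might go further in four ways that the documents do not support:

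- **That the trial relies on this test, or exists to tell the larger trial whether effects vary by injury duration.** G1 and G3 do not list that among the purposes, and no planned conclusion depends on it.
- **That a third to a half of the information is lost as a matter of fact.** This needs a distribution, a split and a linear effect, none of which is in the documents.
- **That the group injured under 2 years will be too sparse in one arm.** Its share is not given. Recruitment uses flyers in rehabilitation facilities as well as the waiting list, and section 2.d stratifies on this factor, so a calculation from simple allocation would not describe the design.
- **That continuous coding cures the low power.** Step 3 of the working shows that it does not.

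What the objection does not remove is that the coding is unspecified, may waste collected data, and comes with no named interval. Exploratory status favours estimation over testing.

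**Conclusion.** The point holds as a minor improvement to an exploratory analysis. If the effect varies smoothly with time since injury, a two-level dummy loses about 36% of the information at a 50/50 split and 51% at 20/80 under a normal moderator and a linear effect. The range is about 25% to 80% across the distributions tried, and the loss is nil for a true step at the cut.

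The interaction test can detect only very large differences: about 1.8 SD unadjusted at an even split and about 1.3 SD with r = 0.7. It would approach 0.8 SD only with r near 0.9 and balanced groups. A non-significant result would therefore say little.

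These conclusions assume that the CORE records time as a date or a number and that the dummy has two levels, probably at 2 years. Both are reasonable inferences, but neither is stated. The coding criticism applies to time since injury; the precision point applies to both moderators.

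**What to change.** In G4:

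- Enter time since injury as a continuous moderator, for example log years. Keep the under-2 versus 2-or-more-years stratum as a sensitivity analysis, and keep the dummy for injury level with its cut stated.
- Report each interaction estimate with its 95% confidence interval. Report the CBEI effect with 95% confidence interval by injury level and at a few times since injury within the observed range.
- Label these results exploratory and state that non-significance is not evidence of a uniform effect.

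The cost is a few sentences and no new data, provided the CORE holds a date or duration; this should be checked against the form. The downside is the assumption of a smooth trend, which 40 people can check only roughly. The change also leaves the interaction test underpowered, so the intervals should carry the message.
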